APPENDIX 6. GENETICS

Use/Analysis of DNA

- Genetic variation may impact a participant's response to study intervention, susceptibility to, and severity and progression of disease. Variable response to study intervention may be due to genetic determinants that impact intervention absorption, distribution, metabolism, and excretion; mechanism of action of the intervention; disease etiology; and/or molecular subtype of the disease being treated. Therefore, where local regulations and IRB/IEC allow, a blood sample will be collected for DNA analysis from consenting participants.
- DNA samples will be used for research related to JZP150 or PTSD and related diseases. They may also be used to develop tests/assays including diagnostic tests related to JZP150. Genetic research may specifically consist of the analysis of one or more candidate genes or the analysis of genetic markers throughout the genome or targeted candidate gene analysis (as appropriate).
- [REDACTED]
- The samples may be analyzed as part of a multi-study assessment of genetic factors involved in the response to JZP150 or study interventions of this class to understand study disease or related conditions.
- The results of genetic analyses may be reported in the clinical study report or in a separate study summary.
- The sponsor will store the DNA samples in a secure storage space with adequate measures to protect confidentiality.
- The samples will be retained while research on JZP150 continues but no longer than 15 years or other period as per local requirements.

APPENDIX 7. LIVER SAFETY: SUGGESTED ACTIONS AND FOLLOW-UP ASSESSMENTS

Table 7: Phase 2 Liver Chemistry Stopping Criteria and Follow-up Assessments

Liver Chemistry Stopping Criteria	
ALT-absolute	ALT $\geq 5 \times$ ULN
ALT Increase	ALT $\geq 3 \times$ ULN persists for ≥ 4 weeks
Total bilirubin^{a,b}	ALT $\geq 3 \times$ ULN and total bilirubin $\geq 2 \times$ ULN ($> 35\%$ direct bilirubin)
INR^b	ALT $\geq 3 \times$ ULN and INR > 1.5 , if INR measured
Cannot Monitor	ALT $\geq 3 \times$ ULN and cannot be monitored weekly for 4 weeks
Symptomatic^c	ALT $\geq 3 \times$ ULN associated with symptoms (new or worsening) believed to be related to liver injury or hypersensitivity
Suggested Actions, Monitoring and Follow-up Assessments	
Actions	Follow-up Assessments

Immediately discontinue study intervention.
 
Record the Liver Stopping Events as an AE, and report to the sponsor or designee as an ORE, as described in Appendix 4.
 
If the Liver Stopping Event also meets the criteria for an SAE, record and report to the sponsor or designee as an SAE, as described in Appendix 4.
 
Perform follow-up assessments as described in the Follow-Up Assessment column.
 
Monitor the participant until liver chemistry test abnormalities resolve, stabilize, or return to baseline (see MONITORING).
 
MONITORING:
 
If ALT $\geq 3 \times$ ULN AND total bilirubin $\geq 2 \times$ ULN or INR > 1.5:
 
Repeat liver chemistry tests (include ALT, AST, alkaline phosphatase, total bilirubin and INR) and perform liver event follow-up assessments within 24 hours.
 
Monitor participant twice weekly until liver chemistry test abnormalities resolve, stabilize, or return to baseline.
	
Viral hepatitis serology.^d
 
Obtain INR and recheck with each liver chemistry assessment until the transaminases values show downward trend.
 
Obtain blood sample for PK analysis.^e
 
Obtain serum creatine phosphokinase, lactate dehydrogenase, GGT, glutamate dehydrogenase, and serum albumin.
 
Fractionate bilirubin, if total bilirubin $\geq 2 \times$ ULN.
 
Obtain complete blood count with differential to assess eosinophilia
 
Record the appearance or worsening of clinical symptoms of liver injury, or hypersensitivity as an AE.
 
Record use of concomitant medications (including acetaminophen, herbal remedies, recreational drugs and other over-the-counter medications) and provide information via email to [contact].
 
If ALT $\geq 3 \times$ ULN AND total bilirubin $< 2 \times$ ULN or INR > 1.5 obtain the following in addition to the assessments listed above:
 
Anti-nuclear antibody, anti-smooth muscle antibody, Type 1 anti-liver kidney microsomal antibodies, and quantitative total immunoglobulin G or gamma globulins.

Liver Chemistry Stopping Criteria	

A specialist or hepatology consultation is recommended.
 
If $ALT \geq 3 \times ULN$ AND total bilirubin $< 2 \times ULN$ and INR ≤ 1.5:
 
Repeat liver chemistry tests (include ALT, AST, alkaline phosphatase, total bilirubin and INR) and perform liver chemistry follow-up assessments within 24 to 72 hours.
 
Monitor participants weekly until liver chemistry abnormalities resolve, stabilize, or return to baseline.
 
Permanently discontinue study intervention and continue participant in the study for any protocol-specified follow-up assessments.
	
Serum acetaminophen adduct assay, when available, to assess potential acetaminophen contribution to liver injury in participants with definite or likely acetaminophen use in the preceding week.
 
Liver imaging (ultrasound, magnetic resonance, or computerized tomography) and/or liver biopsy to evaluate liver disease. Provide liver imagine results via email to [contact].
 
Liver biopsy may be considered and discussed with local specialist if available:
 
In participants when serology raises the possibility of autoimmune hepatitis.
 
In participants when suspected drug-induced liver injury progresses or fails to resolve on withdrawal of study intervention.
 
In participants with acute or chronic atypical presentation
 
If liver biopsy conducted, provide liver imaging results via email to [contact].

^a Serum bilirubin fractionation should be performed if testing is available. If serum bilirubin fractionation is not immediately available, discontinue study intervention if $ALT \geq 3 \times ULN$ and total bilirubin $\geq 2 \times ULN$.

Additionally, if serum bilirubin fractionation testing is unavailable, **record the absence/presence of detectable urinary bilirubin on dipstick which** is indicative of direct bilirubin elevations suggesting liver injury.

^b All events of $ALT \geq 3 \times ULN$ and total bilirubin $\geq 2 \times ULN$ ($> 35\%$ direct bilirubin) or $ALT \geq 3 \times ULN$ and INR > 1.5 may indicate severe liver injury (**possible “Hy’s Law”**) and **must be reported to sponsor in an expedited manner and as an SAE if SAE criteria met**. The INR stated threshold value will not apply to participants receiving anticoagulants.

^c New or worsening symptoms believed to be related to liver injury (such as fatigue, nausea, vomiting, right upper quadrant pain or tenderness, or jaundice) or hypersensitivity (such as fever, rash or eosinophilia).

^d Includes: Hepatitis A immunoglobulin M (IgM) antibody; hepatitis B virus surface antigen (HBsAg) and hepatitis B core antibody (HBcAb); hepatitis C RNA; cytomegalovirus IgM antibody; Epstein-Barr viral capsid antigen IgM antibody (or if unavailable, heterophile antibody or monospot testing); and hepatitis E IgM antibody.

^e PK sample may not be required for participants known to be receiving placebo. Record the date/time of the PK blood sample draw and the date/time of the last dose of study intervention prior to the blood sample draw on the CRF. If the date or time of the last dose is unclear, provide the participant’s best approximation. If the date/time of the last dose cannot be approximated OR a PK sample cannot be collected in the time period indicated above, do not obtain a PK sample. Instructions for sample handling and shipping are in the Investigator Trial Site Binder.

Table 8: Phase 2 Liver Chemistry Increased Monitoring Criteria with Continued Study Intervention

Liver Chemistry Increased Monitoring Criterion and Actions With Continued Study Intervention	
Criterion	Actions
ALT $\geq 3 \times$ ULN and $< 5 \times$ ULN and total bilirubin $< 2 \times$ ULN or INR < 1.5 , without symptoms believed to be related to liver injury or hypersensitivity, and who can be monitored weekly for 4 weeks	Notify the sponsor within 24 hours of learning of the abnormality to discuss participant safety. Participant can continue study intervention. Participant must return weekly for repeat liver chemistry tests (ALT, AST, alkaline phosphatase, total bilirubin) until the abnormalities resolve, stabilize or return to baseline. If at any time, the participant meets liver chemistry stopping criteria, proceed as described in Section 7.1 . If, after 4 weeks of monitoring, ALT $< 3 \times$ ULN and total bilirubin $< 2 \times$ ULN, monitor participants twice monthly until liver chemistry tests resolve, stabilize, or return to baseline.

Signature Page for JZP150-201-02 Protocol Amendment - Published (VV-CLIN-013888)

Approval Task - Approval of Document Signing Verdict/Reason: I Approved This Document	
	16-Nov-2022 18:05:52 GMT+0000

Signature Page for JZP150-201-02 Protocol Amendment - Published (VV-CLIN-013888)

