10.1.9.2. Study/Site Termination

The sponsor or designee reserves the right to close the study site or terminate the study at any time for any reason at the sole discretion of the sponsor. Study sites will be closed upon study completion. A study site is considered closed when all required documents and study supplies have been collected and a study site closure visit has been performed.

Administration of the study agent will be temporarily suspended by the SMT upon the occurrence of any of the following:

- Unexpected SAEs within the same SOC or similar in nature are reported by 2 or more participants on active study intervention with a plausible relationship to study intervention administration.
- 1 or more participants on active study intervention meets Hy's Law Criteria as defined in [Appendix 7](#).

Based on the sponsor review and evaluation of the aforementioned safety events, the study may be restarted or terminated.

The investigator may initiate study site closure at any time, provided there is reasonable cause and sufficient notice is given in advance of the intended termination.

Reasons for the early closure of a study site by the sponsor or investigator may include but are not limited to:

For study termination:

- Sponsor makes a business decision to stop the study.
- Study stopping criteria are met and following investigation, the sponsor decides to stop the study.
- Ongoing evaluation of study safety data suggests that the benefit-risk profile suggests stopping the study.

For site termination:

- Failure of the investigator to comply with the protocol, the requirements of the IRB/IEC or local health authorities, the sponsor's procedures, or GCP guidelines
- Inadequate or no recruitment (evaluated after a reasonable amount of time) of participants by the investigator
- Total number of participants included earlier than expected

If the study is prematurely terminated or suspended, the sponsor shall promptly inform the investigators, the IECs/IRBs, the regulatory authorities, and any contract research organization(s) used in the study of the reason for termination or suspension, as specified by the applicable regulatory requirements. The investigator shall promptly inform the participant and should assure appropriate participant therapy and/or follow-up.

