APPENDIX 3. CLINICAL LABORATORY TESTS

The tests detailed in [Table 6](#) will be performed by the central laboratory, with the exception of urine pregnancy, urine dipstick for drug screen (with the exception of the screening visit during which urine drug screen will be done by the central lab), and breath alcohol tests, which will be performed locally.

Participants are required to fast for safety laboratory tests at the Baseline Visit (Visit 2), Week 1 (Visit 3), Week 4 (Visit 5), Week 12 (Visit 9), Early Discontinuation (Visit 10), if applicable, and Safety Follow-up Visit (Visit 12). Participants are not required to fast for laboratory tests at the Screening Visit or Week 8 (Visit 7).

Local laboratory results are only required in the event that the central laboratory results are not available in time for either study intervention administration and/or response evaluation. If a local sample is required, it is important that the sample for central analysis is obtained at the same time. Additionally, if the local laboratory results are used to make either a study intervention decision or response evaluation, the results must be recorded.

Protocol-specific requirements for inclusion or exclusion of participants are detailed in [Section 5](#) of the protocol.

Additional tests may be performed at any time during the study as determined necessary by the investigator or required by local regulations.

Investigators must document their review of each laboratory report.

Table 6: Protocol-Required Safety Laboratory Tests

Laboratory Tests	Parameters				
Hematology ^a	Platelet Count	RBC Indices: MCV MCH Reticulocytes (count, absolute)	WBC count with Differential: Neutrophils Lymphocytes Monocytes Eosinophils Basophils		
	RBC Count				
	Hemoglobin				
	Hematocrit				
Clinical Chemistry ^{ab}	Albumin	ALP ^c	ALT/ SGPT	AST/ SGOT	
	BUN	Calcium	CO ₂	Chloride	
	Creatinine	Creatine kinase	GGT	Glucose	
				HbA1c (Screening and Week 12 only)	
	Lactate dehydrogenase	Phosphorus	Potassium	Sodium	
	TSH (Screening only)	Total and direct bilirubin	Total cholesterol	Total protein	

Laboratory Tests	Parameters			
	Triglycerides	Uric acid	High-density lipoprotein cholesterol	Low-density lipoprotein cholesterol
	LH (males only)	FSH (collected at Screening only for WONCBP when needed; collected at [REDACTED])	Serum testosterone (males only)	

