- The investigator is obligated to perform or arrange for the conduct of supplemental measurements and/or evaluations as medically indicated or as requested by the sponsor (or designee) to elucidate the nature and/or causality of the AE or SAE as fully as possible. This may include additional laboratory tests or investigations, histopathological examinations, or consultation with other health care professionals.
- New or updated information will be recorded in the originally submitted documents.
- The investigator will submit any updated SAE data to the sponsor or designee within 24 hours of receipt of the information.

Reporting of SAEs

SAE Reporting to Sponsor or Designee via an Electronic Data Collection Tool

- SAEs must be reported to the sponsor (or designee) using an SAE Reporting Form within 24 hours of first knowledge of the event by study personnel.
- The site will enter the SAE data into the electronic system as soon as it becomes available.
- The form, instructions on completion, and contact information can be found in the Investigator Trial Site Binder.
- The SAE Reporting Form should be completed as much as possible before transmittal.
- Contacts for SAE reporting can be found in the Investigator Trial Site Binder.

Reporting of Other Reportable Experiences (OREs) and Adverse Events of Special Interest (AEOSI)

- Other reportable experiences (OREs, including suicidal ideation, overdose, medication error or abuse, and elevated LFTs) and AEOSI requiring expedited reporting, as described in [Section 8.4.6](#),

must be reported to the sponsor or its designee using an ORE/AEOSI Reporting Form within 24 hours of first knowledge of the event by study personnel.

- The form, instructions on completion, and contact information can be found in the Investigator Trial Site Binder.
- The ORE/AEOSI Reporting Form should be completed as much as possible before transmittal.
- Contacts for ORE reporting can be found in the Investigator Trial Site Binder.

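### Table 7's trigger for the extended liver work-up appears to have its bilirubin sign reversed, and so leaves out bilirubin ≥2 × ULN with INR ≤1.5

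*Protocol*

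**What the plan says.** Protocol Appendix 7, Table 7, has an Actions column and a Follow-up Assessments column. The Follow-up column gives a base list for every stopping event: viral serology, INR, PK sample, further chemistry, bilirubin fractionation, blood count, symptoms and concomitant medications including acetaminophen. It then adds a further list for ALT ≥3 × ULN and "total bilirubin $< 2 \times$ ULN or INR > 1.5 obtain the following in addition to the assessments listed above". That further list runs from autoimmune antibodies and immunoglobulins through the acetaminophen adduct assay to liver imaging and/or biopsy.

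The Actions column splits the same participants into two monitoring tiers:

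- The urgent tier (repeat tests within 24 hours, then twice weekly) applies with ALT ≥3 × ULN "AND total bilirubin $\geq 2 \times$ ULN or INR > 1.5". For this tier, "A specialist or hepatology consultation is recommended".
- The lower tier (repeat within 24 to 72 hours, then weekly) applies with ALT ≥3 × ULN and "total bilirubin $< 2 \times ULN$ and INR ≤ 1.5".

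The stopping rows and footnote b treat bilirubin ≥2 × ULN with more than 35% direct, or INR above 1.5, as the severe signals; footnote b labels them possible Hy's Law. Table 8 lets dosing continue under weekly monitoring when ALT is 3 to below 5 × ULN and either bilirubin is below 2 × ULN or INR is below 1.5, provided there are no symptoms and weekly monitoring is possible.

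**The concern.** The work-up trigger matches neither monitoring tier. It pairs the lower tier's bilirubin sign with the upper tier's INR alternative. Read literally, it sends the participant with the least abnormal bilirubin and INR to the extended list and leaves out one with raised bilirubin and normal or near-normal INR.

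The omitted tests look for other causes of liver injury, and their results matter most in a possible Hy's Law case. Under Protocol 10.1.9.2, one such case on active drug suspends dosing, after which: "Based on the sponsor review and evaluation of the aforementioned safety events, the study may be restarted or terminated". The Actions column sends the investigator to the Follow-up column, whose extended list, as printed, excludes that participant.

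**Working it through.** No sample size, power or alpha figure is involved, so the check is a comparison of rules.

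**Step 1. Inputs, all from Table 7.** Let A = ALT ≥3 × ULN, b = bilirubin ≥2 × ULN, i = INR >1.5.

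- Printed work-up trigger: A and (not b, or i)
- Urgent tier: A and (b or i)
- Lower tier: A and not b and not i
- Work-up trigger with the sign changed: A and (b or i)

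Every stopping row requires at least ALT ≥3 × ULN, so A is true throughout. Grouping the printed rule as (A and not b) or i therefore gives the same answers.

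**Step 2. The four combinations.**

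| Bilirubin (× ULN) | INR | Urgent tier | Printed work-up | Sign changed |
|---|---|---|---|---|
| below 2 | ≤1.5 | no | yes | no |
| below 2 | >1.5 | yes | yes | yes |
| ≥2 | ≤1.5 | yes | **no** | yes |
| ≥2 | >1.5 | yes | yes | yes |

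The printed trigger covers 3 of 4 cells and omits 1. It agrees with the urgent tier in 2 of 4 cells; with the sign changed it agrees in 4 of 4.

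**Step 3. What the omitted cell still receives.** Study drug stops if more than 35% of the bilirubin is direct, or if fractionation is not immediately available (footnote a). A participant who stops gets the base list, 24-hour repeat tests, twice-weekly monitoring and the recommended specialist consultation. Only the prompt for the extended list is missing.

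**Step 4. Table 8 (secondary).** Take ALT 3 to below 5 × ULN, no symptoms, weekly monitoring possible and INR measured. Cross three bilirubin levels (below 2; ≥2 with ≤35% direct; ≥2 with >35% direct or not fractionated) with three INR levels (below 1.5; above 1.5 without anticoagulant; above 1.5 on anticoagulant). Footnote b exempts anticoagulated participants from the INR threshold. Of the 9 cells, 5 meet a Table 7 bilirubin or INR stop and 4 do not.

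| Table 8 wording | Cells admitted | Stop cells admitted | Non-stop cells missed |
|---|---|---|---|
| Current: either condition | 5 | 2 | 1 |
| Both conditions | 1 | 0 | 3 |
| No Table 7 stopping criterion met | 4 | 0 | 0 |

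The two stop cells admitted now are bilirubin below 2 × ULN with INR >1.5 off anticoagulant, and bilirubin ≥2 × ULN (>35% direct or not fractionated) with INR below 1.5. Section 7.1.1 and Table 8's own pointer to the stopping criteria make stopping prevail in both.

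**The case against.** **One sign in a machine-read table.** The documents do not state the intended sign. An extraction error is unlikely, because the ≥ sign is read correctly elsewhere in the same cell (the instruction on bilirubin fractionation), but it cannot be excluded. This stands and limits confidence to medium.

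**Extent of the conditional list.** The adduct assay, imaging and biopsy items follow a page break with indentation lost, and the biopsy items carry their own indications. The natural reading is that the condition governs the rest of the list. On the narrowest reading it governs only the antibody and immunoglobulin item, and the same cell is still omitted.

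**The lower-tier cell is not trivial.** Bilirubin below 2 × ULN with INR ≤1.5 still includes ALT ≥5 × ULN, persistent elevation and symptomatic cases, all of which require stopping. Whether the extended work-up is excessive there is a clinical judgement. This stands, and it is why the choice between the two corrections belongs to the medical team. Neither correction keeps the present omission.

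**Practical effect.** The table section is headed "Suggested Actions, Monitoring and Follow-up Assessments". Appendix 4 obliges the investigator to arrange "supplemental measurements and/or evaluations as medically indicated or as requested by the sponsor", and Appendix 3 says "Additional tests may be performed at any time during the study as determined necessary by the investigator". A site with such a case is sent to the Follow-up column within 24 hours and may notice the conflict. All of this stands: the tests remain obtainable. It does not make the printed trigger consistent with the rest of the table.

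**Table 8.** No one should continue dosing wrongly, because stopping prevails. INR is not in the routine panel (Table 6) or in Table 8's weekly tests, so several of the nine cells would often not be distinguishable. The point is fairly called secondary.

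**Conclusion.** The concern holds, as a minor point. On the text as read, the work-up trigger contradicts the urgent tier, the bilirubin stopping row and footnote b. Acetaminophen use is recorded for every stopping event, so on that question only the adduct assay depends on the trigger. Nothing in the efficacy analysis or the safety stopping rules moves.

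The conclusion rests on two assumptions: that the printed PDF carries the same sign as the extracted text, and that the work-up was meant to follow the severe signals used everywhere else in the table.

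**What to change.** 1. Check the sign in the source PDF and confirm the intent with the sponsor's medical team.
2. Change the Table 7 work-up trigger to ALT ≥3 × ULN with total bilirubin ≥2 × ULN or INR >1.5. This also removes the prompt from the cell with bilirubin below 2 × ULN and INR ≤1.5. If the medical team wants the work-up kept there, delete the bilirubin/INR condition so that the list applies to every stopping event.
3. Optionally, reword the Table 8 criterion as ALT ≥3 and below 5 × ULN with no Table 7 stopping criterion met. This wording also settles an INR of exactly 1.5, which Table 8's INR limit excludes and Table 7's INR stop does not catch. Do not simply require both conditions. That would drop from weekly monitoring participants with bilirubin ≥2 × ULN and ≤35% direct (for example known Gilbert syndrome, which exclusion 23 allows) and anticoagulated participants with INR above 1.5.

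The cost is one sign and, optionally, one phrase, by clarification letter or at the next amendment. The SAP, stopping rules and data collection forms need no change. The SAP is dated 12 December 2023; if dosing has already ended, the benefit is to later JZP150 protocols that reuse this appendix.

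### Appendix 7 Table 8 joins its bilirubin and INR limits with 'or', so a participant past exactly one limit meets both a Table 7 stopping row and the criterion for continuing study drug

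*Protocol*

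**What the plan says.** Protocol Appendix 7 has two tables for raised liver chemistry.

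**Table 7 (stopping).** Two of its rows matter here. The bilirubin row is "ALT $\geq 3 \times$ ULN and total bilirubin $\geq 2 \times$ ULN" with more than 35% direct. The INR row is ALT ≥3 × ULN with "INR > 1.5 , if INR measured". Meeting any row leads to "Immediately discontinue study intervention". Footnote a says that if fractionation is not immediately available, total bilirubin alone decides. Footnote b says that the INR threshold does not apply to participants on anticoagulants, and calls both patterns possible Hy's Law.

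**Table 8 (more monitoring, drug continues).** It covers ALT of at least 3 but below 5 × ULN with "total bilirubin $< 2 \times$ ULN or INR" below 1.5, "without symptoms believed to be related to liver injury or hypersensitivity, and who can be monitored weekly for 4 weeks". The action cell says "Participant can continue study intervention". The same cell asks for sponsor notification within 24 hours, sets weekly repeat tests (ALT, AST, alkaline phosphatase, total bilirubin), and sends anyone who meets the stopping criteria to Section 7.1.

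**Elsewhere.** Table 7's monitoring text describes participants below both limits with 'and': "AND total bilirubin $< 2 \times ULN$ and INR" ≤1.5. Sections 7.1 and 7.1.1 make discontinuation mandatory once a liver stopping criterion is met.

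**The concern.** Table 7 needs only one high value to stop drug. Table 8 needs only one low value to allow it. A participant with one of each therefore satisfies both, and the two tables prescribe different actions. For bilirubin ≥2 × ULN or INR >1.5, Table 7 requires an immediate stop, repeat tests within 24 hours and twice-weekly monitoring. Table 8 allows continued drug with weekly tests.

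The profiles concerned are the ones that footnote b labels possible Hy's Law, so the contradiction lies in an operative safety rule. It is in the current protocol text and not in a summary of superseded wording.

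**Working it through.** No figure in the plan is at issue, so the check is logical.

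**Inputs.** Table 7 bilirubin and INR rows with footnotes a and b; the Table 8 criterion, read as ALT range and (bilirubin <2 × ULN or INR <1.5).

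**Held fixed.** ALT 3 to <5 × ULN, raised for less than 4 weeks; no symptoms; can be monitored weekly; not on anticoagulants.

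| Total bilirubin | INR not measured | INR <1.5 | INR = 1.5 | INR >1.5 |
|---|---|---|---|---|
| <2 × ULN | Table 8 | Table 8 | Table 8 | **both** |
| ≥2 × ULN, >35% direct or not fractionated | Table 7 | **both** | Table 7 | Table 7 |
| ≥2 × ULN, ≤35% direct | neither | Table 8 | neither | Table 7 |

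**Examples of the two 'both' cells.**
- ALT 4 ×, bilirubin 2.5 × (>35% direct), INR 1.2. The Table 7 bilirubin row is met; Table 8 is met through INR.
- ALT 4 ×, bilirubin 1.0 ×, INR 2.0. The Table 7 INR row is met; Table 8 is met through bilirubin.

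**Grid count.** Both tables were coded as rules over ALT (2, 3, 4, 4.99, 5, 6 × ULN), bilirubin (1, 1.99, 2, 3 × ULN), direct fraction (20%, 50%), INR (missing, 1.0, 1.49, 1.5, 1.51, 2.0), and symptoms, monitorability and 4-week persistence (each yes/no). Profiles that meet Table 8 and the Table 7 bilirubin or INR row:
- Bilirubin route: 3 ALT values × 2 bilirubin × 1 direct fraction × 2 INR × 2 persistence = 24.
- INR route: 3 × 2 × 2 × 2 × 2 = 48.
- Total: 24 + 48 = 72.

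With 'and' in Table 8, used only as a comparison, the count is 0. These are counts of grid points, not frequencies. The grid leaves out the unfractionated and anticoagulant provisions.

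**Source of the overlap.** Table 7's monitoring branches are exact complements: not (bilirubin ≥2 or INR >1.5) equals bilirubin <2 and INR ≤1.5. Table 8's 'or' is instead the complement of bilirubin ≥2 *and* INR ≥1.5, so on these two tests it excludes only participants who are low on neither.

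**Gaps.** The table already shows two 'neither' cells. A plain swap to 'and' would add three more: bilirubin ≥2 × ULN with ≤35% direct and INR <1.5; bilirubin <2 × ULN with INR exactly 1.5; and, read strictly, bilirubin <2 × ULN with no INR result.

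**INR boundaries.** Table 7's stopping row uses >1.5, its lower monitoring branch ≤1.5, and Table 8 <1.5.

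**The case against.** The strongest reply is that the protocol already resolves the conflict. Section 7.1 says that a participant who meets the liver stopping criteria must be discontinued, Section 7.1.1 says that this is required, and Table 8's wording is only permissive. Its action cell also sends anyone who meets a stopping criterion to Section 7.1, which includes the first qualifying result. Read together, both examples end in a stop. This stands, and it limits the practical risk.

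The second reply is reach. INR is not among the routine tests in Appendix 3 Table 6, and Table 7 obtains it as follow-up to a stopping event. In the bilirubin case the stop would therefore ordinarily come before the INR result. Without an INR result the two tables do not overlap on these rows. This also stands. But Table 8's weekly tests do not list INR, so they cannot by themselves show that a participant admitted on low bilirubin has passed the INR limit.

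Third, the 'or' may have a use. Exclusion criterion 23 admits known Gilbert syndrome with isolated bilirubin above 2 × ULN. With ≤35% direct bilirubin and INR <1.5, such a participant at ALT 4 × ULN meets no immediate stopping row and reaches Table 8 only through INR. The documents do not give this as the purpose, but it shows why removing the overlap is not enough.

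What the reply leaves untouched is the criterion itself. The redirect suits people who later reach a stopping criterion; the 'or' admits people who already meet one.

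**Conclusion.** The contradiction is real and narrow. At ALT 3 to <5 × ULN it affects participants past exactly one of the two limits, with an INR result, without symptoms and able to be monitored weekly. The high-bilirubin case also needs >35% direct or no immediate fractionation; the high-INR case needs the participant not to be on anticoagulants. The documents give no expected number of such participants.

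A reader might infer more, but the documents do not support it:
- *That every Table 7 criterion overlaps Table 8.* ALT ≥5 × ULN, symptoms, inability to monitor, and both limits exceeded all fall outside Table 8 on the reading used here. The row for ALT ≥3 × ULN lasting at least 4 weeks does overlap, but with either connector, so that is a separate matter of timing.
- *That a site would keep such a participant on drug.* The mandatory stop and the 24-hour sponsor contact point the other way.
- *That Table 7's two monitoring branches conflict.* They are complements.
- *That the suspension rule in Section 10.1.9.2 turns on Table 8.* It turns on the Hy's Law criteria in Appendix 7.

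The conclusion rests on bracketing the bilirubin and INR limits together, which is the narrower reading. Taking 'or' at strict logical precedence would also admit ALT ≥5 × ULN through INR, but the point does not need it.

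**What to change.** Reconcile the Table 8 criterion with the Table 7 bilirubin and INR rows, including footnotes a and b, so that at ALT 3 to <5 × ULN:

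1. no profile meets both an immediate stopping row and the continue criterion; and
2. no profile falls in neither table. Bilirubin ≥2 × ULN with ≤35% direct, INR exactly 1.5 and INR not measured each need an explicit place.

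Align the three INR boundaries, and state how the INR limit is to be judged when the weekly tests do not include INR. Also check the Table 7 follow-up column, where the additional tests are triggered, as printed, by bilirubin <2 × ULN or INR >1.5. That pairs the low side of one limit with the high side of the other. Which clinical rule applies is for the sponsor's medical team.

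The cost is a short rewording of Appendix 7 by clarification letter or amendment, somewhat more than a change of one connector. The documents do not say whether dosing is complete; the SAP is dated 12 December 2023. If it is complete, the equivalent step is to review how each case of ALT ≥3 × ULN was handled. The listing in SAP Section 10.3 (ALT or AST ≥3 × ULN with total bilirubin >2 × ULN) would show the high-bilirubin cases, except bilirubin at exactly 2 × ULN. It has no INR term, so high-INR cases need a separate look.
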